Data Management: Vaccination data will be retrieved from EzVac. All data will be accessed using a password-protected computer in a locked office and stored on a secure server managed by Columbia University IT, and backed up on a daily basis. All data files will be cleaned and edited prior to analysis, under [name] supervision. Data analysis will be performed using SAS (Cary, NC). The programmer will monitor log files of text messages sent, replies received, and "undeliverable" messages and provide summaries to [name] on a daily basis.

Statistical Procedures

Data Analysis: We will first assess the randomization process by comparing baseline variables among the three groups. Hypothesis: Completion and timeliness will be higher in adolescents in families who receive enhanced text message reminders plus usual care vs. non-enhanced text message reminders plus usual care.

Series Completion: HPV vaccine completion rates in EzVac will be compared for all adolescents of participant parents at the end of a 12-month observation period starting at receipt of their first HPV vaccine dose. As in our previous RCT of influenza vaccine reminders,¹³ all primary analyses will be done on an intention-to-treat basis, such that all randomized participants will be included in the analysis whether or not they at some point declined further messages or messages were returned as undeliverable. A secondary analysis will compare completion rates for adolescents of participants who received the entire set of reminders. Study arms will not be combined. Completion rates in the two randomized groups will be compared in the separate combinations delineated above using 2-sided 2 tests at a significance level of $P<0.05$ for each comparison. The number of subjects in each cell is expected to be high enough that the Fisher exact test will not be needed. Asymptotic confidence limits on the differences and relative rate ratios will be calculated.

Sub-group Analyses: We will perform subgroup analyses in different covariate-defined subgroups, for each outcome, to assess the possibility of intervention effects being different in these subgroups. This will be tested by including pre-specified covariates (adolescent: age, gender, year of entry, clinic site, dichotomized visit count; parent: language, previous participation in text message vaccination reminder study),^{42,43,60,61,64-}

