⁶⁸ and their interactions with the intervention in a multiple logistic regression analysis. The models will also adjust for the direct effects of these covariates on the outcomes, thus increasing power to detect intervention effects. Initial models will be created including all of these covariates. Clearly non-significant ($p>0.2$) covariate terms will be removed from the final models. If more than one covariate appears in a final model, two-way (and, if necessary, multi-way) interactions of those covariates among themselves and with the study arm will be tested and included if significant at $p>0.2$) covariate terms will be removed from the final models. If more than one covariate appears in a final model, two-way (and, if necessary, multi-way) interactions of those covariates among themselves and with the study arm will be tested and included if significant at $p<0.05$. In addition to the covariates listed above, we will include race and insurance to the extent possible. Multivariate modeling with these covariates may not be possible depending on the degree of variability observed. The visit count will be defined as the number of clinic visits per adolescent in the 12-month period post-receipt of the first vaccine dose. Visits to the emergency department, hospitalization or specialty visits will not be included. The visit count will be dichotomized (the cut point determined by the frequency distribution of visit counts). With regard to longitudinal measurement, the outcome is defined as success or failure in receipt of 3 HPV vaccine doses within 12 months (no repeat measure of outcome). We will include a covariate for year of entry into study. We will also adjust for vaccine shortages as needed.

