Timeliness: We define timeliness of vaccination according to the ACIP recommended intervals.⁶⁹ We will construct Kaplan-Meier curves of time from first to second dose and separately first to third dose,⁷⁰ using both intention to treat as well as analyses accounting for message deliverability. We will then compare the curves using a log rank test. We will perform secondary subgroup analyses using Cox proportional hazards modeling to examine subgroup effects and to adjust for the same covariates as described above. Interactivity of messages: With regard to analyses pertaining to the interactive nature of messages in Arm 1, we will calculate the proportion of families who sought information about each individual topic both for the overall arm as well as subdivided by gender and parental language and stage of HPV vaccine decision-making at baseline. We will use Pearson's chi square to compare completion rates at 12

months in adolescents in Arm 1 whose families requested further information vs. those in Arm 1 who did not.

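### The subgroup models select interactions at an unadjusted p<0.05: about a 30% chance of a false subgroup effect per outcome from 7 arm-by-covariate tests, rising to 76% only in the full three-way search

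*Combined protocol and SAP*

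**What the plan says.** The rule is in Statistical Procedures, under Sub-group Analyses. Its scope is set by "We will perform subgroup analyses in different covariate-defined subgroups, for each outcome". The covariates are "adolescent: age, gender, year of entry, clinic site, dichotomized visit count; parent: language, previous participation in text message vaccination reminder study", seven in all, entered together with main effects "and their interactions with the intervention in a multiple logistic regression analysis". Race and insurance may be added if the data allow.

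The model is then built in steps:

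- Screen: "Clearly non-significant ($p>0.2$) covariate terms will be removed from the final models".
- Condition for the search: "If more than one covariate appears in a final model".
- Search: "two-way (and, if necessary, multi-way) interactions of those covariates among themselves and with the study arm will be tested and included if significant at" p<0.05.

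The search sentence appears twice. In the first copy it runs into the p>0.2 text, and only the second copy gives 0.05. I read 0.05 as the rule and the repeat as a text fault.

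The section says that adjusting for the covariates' direct effects raises power: "thus increasing power to detect intervention effects". Under Timeliness, the plan adds: "We will perform secondary subgroup analyses using Cox proportional hazards modeling to examine subgroup effects", adjusting for the same covariates.

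The primary comparison is a separate two-sided test of completion rates in all randomized participants (Series Completion; Missing data).

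**The concern.** The covariates are named in advance, but the interactions that reach the final model are chosen by their p-values. The plan gives no criterion for going beyond two-way terms, no adjustment for the number of tests, no exploratory label, and no commitment to report interactions that were not significant. A reader of the final model would see the selected terms without knowing how many were tried.

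Two things are at stake. The first is a claim that the enhanced messages work differently by, say, site, language or gender when they do not. The Message Design section reports that the team's earlier studies found no interaction with message language or with gender, so a lone hit on either would need caution. The second is the adjusted treatment effect. If an arm interaction has been selected, the arm coefficient may no longer be an overall effect, and the plan does not say which model supplies one.

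**Working it through.** **The plan's own figure.** Study Sample and Enrollment gives 478 per arm for 51% against 60% (a 9-point difference), 80% power and 5% type I error. With pooled variance and no continuity correction:

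n = [1.960·√(2·0.555·0.445) + 0.842·√(0.51·0.49 + 0.60·0.40)]² / 0.09² = (1.377 + 0.589)² / 0.0081 ≈ 477.5, so 478 per arm.

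This reproduces. The plan gives no error rate or count of tests for the subgroup search.

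**Counting arm-involving tests.** Count one joint test per covariate or covariate pair. With k covariates kept, there are k arm two-way terms and k(k−1)/2 arm three-way terms. Covariate-by-covariate terms do not involve the arm and are not counted.

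**Chance of at least one false hit**, with no true heterogeneity and m independent tests at 0.05: 1 − 0.95^m.

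- Two-way arm terms only, seven covariates: 1 − 0.95^7 = 30.2%. With nine covariates (race and insurance added): 37.0%.
- Two- plus three-way arm terms, by number of covariates kept:

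| k kept | two-way | three-way | total m | chance |
|---|---|---|---|---|
| 2 | 2 | 1 | 3 | 14.3% |
| 3 | 3 | 3 | 6 | 26.5% |
| 4 | 4 | 6 | 10 | 40.1% |
| 5 | 5 | 10 | 15 | 53.7% |
| 6 | 6 | 15 | 21 | 65.9% |
| 7 | 7 | 21 | 28 | 76.2% |
| 9 | 9 | 36 | 45 | 90.1% |

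The 50% line is crossed at 14 tests (51.2%). If all seven first-step two-way tests are counted and three-way terms are added only among the covariates kept, k = 4 gives 13 tests (48.7%) and k = 5 gives 17 (58.2%). If every order of arm interaction is tested (2^k − 1 terms), k = 4 gives 15 tests (53.7%).

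**Does independence matter?** In simulated trials (N = 956, seven covariates, no true interaction, 500 runs per scenario, covariate distributions assumed), the 7 two-way tests gave at least one false hit in 28–30% of trials and all 28 tests in 74–77%. The formula is adequate.

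**Effect of the p>0.2 screen.** This depends on how strongly the covariates predict completion. The same simulations, with the screen followed by two- and three-way testing, gave:

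- no covariate effects: 8% (mean 1.4 covariates kept)
- log-odds 0.2: 34% (mean 3.7 kept)
- log-odds 0.4: 70% (mean 6.4 kept)

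A separate simulation (400 trials per scenario, backward removal, no arm effect) gave 12%, 64% and 83% for covariate odds ratios of 1.0, 1.3 and 1.6. With two-way arm terms alone it gave 8%, 29% and 33%.

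The documents give one relevant figure. Under Preliminary Studies, 12-month completion was 40.0% in females and 30.7% in males, an odds ratio of (0.400/0.600)/(0.307/0.693) ≈ 1.5.

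**Meaning of the arm coefficient.** Under reference coding, an arm-by-covariate term makes the arm coefficient the effect at the reference level.

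- One balanced binary covariate: half the sample informs the coefficient, so its standard error rises by √2 = 1.41. The planned effect is 1.96 + 0.84 = 2.80 standard errors; 2.80/1.41 = 1.98, and power is Φ(1.98 − 1.96) ≈ 51%.
- Four equal sites: the standard error doubles; 2.80/2 = 1.40, and power is Φ(1.40 − 1.96) ≈ 29%.
- Effect coding with balanced strata: the arm term is the average effect across strata, and power stays at 80%.

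**The case against.** The strongest reply is that the primary conclusion does not depend on any of this. It comes from a separate unadjusted intention-to-treat comparison. The covariates are pre-specified, and the subgroup aim is worded cautiously, as assessing a possibility. All of that stands and limits the severity.

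A reader might infer that the plan commits to at least 28 arm-involving tests. It does not. The screen comes first, and multi-way terms are conditional, so the firm count is 7. A reader might also infer that a false subgroup effect is more likely than not once multi-way terms are tested. With testing up to three-way terms, that needs about five covariates kept; if every order is tested, it needs four. The documents do not give the covariate strengths that decide how many survive. The gender figures, and a visit count taken over the same 12 months as the later doses, suggest that some covariates will survive, but not how many.

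The power losses are also conditional. They apply to a reference-coded coefficient after an interaction has been kept. The plan does not specify coding, and no sentence says that such a coefficient will be reported as the overall effect. The power sentence concerns covariate main effects. What remains is that the same model-building sequence goes on to add arm interactions without saying how an overall effect would then be obtained.

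The extension to the Cox models is partly inferred. Timeliness imports the covariates but does not restate the search; support comes from the general statement that subgroup analyses apply to each outcome.

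**Conclusion.** The concern holds as a matter of multiplicity and of an undefined adjusted effect in the secondary models. Assuming no true heterogeneity, independent tests and one test per term, the 7 arm-by-covariate tests give about a 30% chance of at least one false subgroup effect per outcome. Two- plus three-way arm terms give 14–40% with two to four covariates kept. The 76% figure needs all seven kept and every three-way arm term tested. Simulations of the full sequence run from 8% to 83% depending on assumed covariate effects, so no single figure can be attached to the plan as written.

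If an arm interaction is kept and reference coding is used, the arm coefficient is a reference-subgroup effect with a standard error about 1.4 times larger for one balanced binary covariate. That model then does not directly give the overall adjusted effect or the power gain that the section describes. The primary test keeps its error rate and power. The change should be made, but it does not bear on the validity of the main result.

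**What to change.** In Sub-group Analyses, delete the sentence removing covariate terms with p>0.2 and both copies of the interaction-search sentence. Leaving the removal sentence in place would contradict a model with all main effects. Replace them with:

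*Effect modification will be tested only as study arm by each pre-specified baseline covariate (age, gender, year of entry, site, language, previous participation), one at a time, in a model with arm and all baseline covariate main effects. All interaction estimates and 95% CIs will be reported whatever their p-value and labelled exploratory, unless significant after multiplicity adjustment across the list. No covariate-by-covariate or multi-way interaction will be selected into the model. The adjusted overall arm effect will be taken from the model with baseline covariates and no arm interactions. Visit count, measured after the first dose, will not be in that model and will be reported only as a separate descriptive analysis.*

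Apply the same rule to the Cox models under Timeliness. Visit count is set apart because the plan counts visits over the 12 months after dose 1, when reminders can change them. Six unadjusted tests would still carry 1 − 0.95^6 = 26.5%, which is why the exploratory label or an adjustment (for example Bonferroni, 0.05/6 = 0.0083) is needed; either will do.

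The cost is wording only. The downside is less sensitivity to a genuine complex interaction.

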We will identify in EzVac those who received their first HPV vaccine in approximately the last week for whom we do not have a card. On inclusion, either via return of the enrollment card or over the phone, a confirmation text message will be sent to the participant family and delivery status assessed to ensure that the family has a working cellphone with text message. An undelivered message will be attempted to be delivered twice moreover the next week. If there are three undeliverable messages then the family will not be considered to have met eligibility criteria and will not be considered enrolled in the trial; they will be notified of this. We will enroll only one child per family. If more than one is eligible, we will select the one with the next most proximal birthday, e.g. a child whose birthday is in 7 days will be selected over a sibling whose is in 75 days. In the case of twins, whoever was designated at birth as twin A will be enrolled. If another adolescent becomes eligible during the trial, the family cannot re-enroll.

Randomization: Randomization will occur with a 1:1 allocation ratio stratified by (1) clinical site; (2) adolescent's gender; (3) parental language; and adolescent's age group (9-14; 15-17). These factors will be excerpted from the medical record after enrollment. Randomization will be done centrally by the programmer using an algorithm based on site, gender, language, and age. The statistician and analyst will be kept blinded to group assignment.

Study Sample and Enrollment

Based on EzVac data, there were 817 adolescents (females and males) 11-17 years old who received their first HPV vaccine at the four study sites between October 2012 and September 2013. Nearly all of those families (n=805) spoke English or Spanish. A few (n=51) were from the same family. Therefore, we expect 1885 adolescents to be eligible over the 30-month recruitment period. Across various studies conducted at the study sites, we found that between 83% and 89% of parents had text messaging. In one study, we assessed those with and without text messages and found no significant differences between those who had texting and those who did not in terms of adolescent's gender, parents' primary language, education level, or parent age. Using the low-end of this range, i.e. 83%, we expect 1,564 families to meet age, language and cell phone/texting inclusion criteria. To meet our sample size of 956 total (478 per arm), we would need to

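### The p>0.2 covariate screen decides which arm-by-covariate interactions are tested, so pre-specified subgroups can go unexamined and stratification factors can leave the adjusted models

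*Combined protocol and SAP*

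**What the plan says.** All references are to the combined protocol and SAP.

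Under Statistical Procedures, Sub-group Analyses, the purpose is "to assess the possibility of intervention effects being different in these subgroups". The covariates are listed as "adolescent: age, gender, year of entry, clinic site, dichotomized visit count; parent: language, previous participation in text message vaccination reminder study". The opening sentence says the test will be made by including these covariates "and their interactions with the intervention in a multiple logistic regression analysis".

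The same section then gives a sequence:

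1. "Initial models will be created including all of these covariates". This sentence does not mention interactions.
2. "Clearly non-significant ($p>0.2$) covariate terms will be removed from the final models". No covariate is exempted here, although a later sentence separately says that year of entry will be included.
3. If more than one covariate is left, "interactions of those covariates among themselves and with the study arm will be tested", and interactions are kept at p<0.05.

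The Randomization paragraph states: "Randomization will occur with a 1:1 allocation ratio stratified by (1) clinical site", followed by adolescent gender, parental language and age group. All four correspond to covariates on the screened list. The Timeliness paragraph carries the same covariates into secondary Cox models. The primary comparison, under Series Completion, is an unadjusted two-sided test of two completion rates.

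**The concern.** The screen acts on each covariate's average association with completion. The subgroup question is whether the arm difference varies with the covariate. A covariate can have almost no average association and still modify the effect. Under the stepwise rule, that covariate is removed and its arm interaction is never looked at. If exactly one covariate survives, the rule does not call for its interaction to be tested either.

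Two things are at stake. First, subgroups that were pre-specified become selected on the outcome data, and a subgroup missing from the report could mean either that no interaction was found or that none was tested. Second, the rule can remove stratification factors from the adjusted logistic models and, by reference, from the Cox models.

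**Working it through.** **The plan's own figure.** Study Sample and Enrollment gives 478 per arm for a 9-point difference from 51%, with 80% power and 5% type I error. Using the pooled formula without continuity correction and a mean rate of 0.555:

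n = [1.96 × √(2 × 0.555 × 0.445) + 0.8416 × √(0.51 × 0.49 + 0.60 × 0.40)]² / 0.09² = 477.5, so 478 per arm and N = 956.

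This reproduces exactly. The subgroup plan has no power figure of its own.

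**Chance of being screened out.** Assume a binary covariate split 50:50 (the documents give no splits for the trial) and an overall rate of 55.5%.

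- SE of the average gap = √(4 × 0.555 × 0.445 / 956) = 3.2 points.
- The two-sided p>0.2 boundary is |z| < 1.2816.
- P(drop) = Φ(1.2816 − gap/SE) − Φ(−1.2816 − gap/SE).

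| Average gap | gap/SE | P(drop) |
|---|---|---|
| 0 points | 0 | 80% |
| 2 points | 0.62 | 72% |
| 5 points | 1.56 | 39% |

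**Three shapes of effect modification.** Assume control rates of 56% in females and 46% in males (mean 51%, as the plan expects for Arm 2), an enhanced-arm mean of 60%, and 239 per cell. SE of the interaction = √(Σp(1−p)/239), which is 6.4 points in each case. SE of the average gap is half of that, 3.2 points.

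| Enhanced arm (F/M) | Average gap | P(drop) | Interaction | Power if tested directly |
|---|---|---|---|---|
| Halves the gap: 62.5/57.5 | 7.5 | 14% | 5 | 12% |
| Closes it: 60/60 | 5 | 39% | 10 | 35% |
| Reverses it: 57/63 | 2 | 72% | 16 | 71% |

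In a balanced design the average gap and the interaction are estimated nearly independently. The chance of both surviving the screen and being detected is therefore close to the product: 0.12 × 0.86 = 10%, 0.35 × 0.61 = 21% and 0.71 × 0.28 = 20%. A simulation of the third row (20,000 runs; logistic screen, then Wald interaction test) agrees: 72% dropped, and power falls from 71% to 20%.

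**Two bounding cases** (simulation, 4,000 runs each; effect 0 in one half and +18 points in the other):

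- Equal control rates of 51%: dropped in 7% of runs; power 83% directly, 78% after the screen.
- No average gap: dropped in 80% of runs; power 81% directly, 16% after the screen.

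**The more-than-one condition.** If all seven listed covariates had null main effects (independent, one degree of freedom each), at most one would survive with probability 0.8⁷ + 7 × 0.2 × 0.8⁶ = 0.210 + 0.367 = 58%, and no interaction would then be tested. If year of entry is always kept, this needs all six others to be dropped: 0.8⁶ = 26%.

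**Strata.** If all four had null main effects on the same assumptions, at least one would be dropped with probability 1 − 0.2⁴ = 99.8%.

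**The case against.** The opening sentence of the section says the interactions are included, so an analyst might put them in the initial model. That is a fair reading of that sentence. It does not settle the matter, because the later steps test interactions only among covariates that remain. The section contradicts itself, and the pre-specified procedure is unclear. A reader might go further and infer that, under this alternative, main effects would be removed while their interactions stay. The plan does not say so.

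A reader might also infer that the screen defeats the subgroup analysis, or that a covariate is likely to be discarded whenever the messages help most where completion is lowest. The figures do not support either claim. Halving a 10-point gap leads to removal only 14% of the time, and closing it completely 39%; it takes a reversal to reach 72%. Preliminary Studies reports site gaps between the sexes of 40.0 − 30.7 = 9.3 points and 56.8 − 45.6 = 11.2 points, so gender may well survive. Where the interaction itself creates a clear average gap, the loss is small (83% to 78%). Direct tests of modest interactions also have little power (12% and 35% above).

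The strata point reaches only secondary models. Finally, the repeated fragment that appears to admit interactions at p>0.2 looks like a copying fault and is not counted here.

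**Conclusion.** The point holds as a defect in the secondary analyses. The stepwise rule makes the test for effect modification depend on a different quantity, and it conflicts with both the stated purpose and the opening sentence of the same section. The cost varies: negligible when the covariate has a clear average gap, and large when it has little or none (80% removed at a gap of zero). The same rule leaves site, gender, language and age group unprotected in the adjusted logistic and Cox models; year of entry has its own inclusion sentence.

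It would be wrong to infer that the primary result is at risk, since that comparison is unadjusted. The percentages rest on assumed 50:50 splits, one-degree-of-freedom covariates and illustrative subgroup rates. Site has four levels, and an unequal split changes the figures: at 20:80, a 5-point gap is dropped 51% of the time instead of 39%.

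**What to change.** 1. Test the arm interaction for each pre-specified baseline covariate, regardless of its main-effect p-value and of how many covariates remain. Report every subgroup estimate with its confidence interval and interaction p-value, labelled exploratory. Bring the opening sentence and the stepwise text into line with this.
2. Do not present visit count as a baseline subgroup factor. The plan counts visits over the 12 months after the first dose, so the messages could affect it.
3. Keep site, gender, language and age group in all adjusted logistic and Cox models regardless of significance.

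The cost is SAP wording, a few more model fits and a longer table of mostly null interactions. Multiplicity is a real downside: seven independent tests at 0.05 carry a 1 − 0.95⁷ = 30% chance of at least one false positive (26% for six, with visit count left out), hence the exploratory label. The degrees of freedom used by the retained strata are negligible with 956 participants.
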